Official Study Title

A Prospective Study Assessing Neurological Function and Its Clinical Implications in Patients With Locally Advanced or Metastatic Urothelial Carcinoma Receiving Enfortumab Vedotin-Based Therapy

ClinicalTrials.gov Identifier (NCT Number): Pending Assignment

Document Date: June 27, 2025

Confidentiality Notice:

This document is intended for use in the ClinicalTrials.gov registration and results reporting process only. It does not contain any personal identifiers of study participants.

1. Official Study Title

A Prospective Study Assessing Neurological Function and Its Clinical Implications in Patients With Locally Advanced or Metastatic Urothelial Carcinoma Receiving Enfortumab Vedotin-Based Therapy

2. Background and Rationale

Locally advanced or metastatic urothelial carcinoma (la/mUC) remains a highly lethal disease despite advances in systemic therapy. While platinum-based chemotherapy (Plt-ChT) has long been the mainstay of first-line treatment, its survival benefit is limited by significant toxicity and a lack of durable response. Enfortumab vedotin (EV) is a NECTIN-4-directed antibody-drug conjugate (ADC) that has demonstrated robust antitumor activity in patients with la/mUC. In the phase III EV-301 study, EV significantly improved overall survival in patients who progressed following Plt-ChT and ICIs. More recently, the phase III EV-302 trial established EV in combination with pembrolizumab as a superior first-line therapy compared to Plt-ChT, regardless of cisplatin eligibility. Based on these data, EV has been approved in both first-line (in combination) and third-line (monotherapy) settings and is considered a standard of care in la/mUC.

However, peripheral neuropathy (PN), a known adverse event associated with the payload monomethyl auristatin E (MMAE), remains a major dose-limiting toxicity of EV. PN occurs in 40–50% of patients, can be irreversible, and significantly impairs patients' quality of life. Although the underlying mechanisms are not fully elucidated, they may include both on-target and off-target effects, such as MMAE-induced microtubule disruption, premature drug release, and neuroinflammatory processes. Notably, the lack of objective tools for early identification and quantitative monitoring of EV-induced PN poses a clinical challenge.

This study aims to prospectively assess neurological function in patients receiving EV-based therapy for la/mUC. By correlating objective neurological assessments with patient-reported outcomes, we seek to improve the understanding of EV-related PN, identify high-risk individuals, and lay the groundwork

for future preventive or mitigating strategies. The findings may ultimately contribute to optimizing EV-based treatment by balancing efficacy with tolerability.

3. Objectives

3-1. Primary Objective

(1) To investigate the correlation between neurological function and subjective symptoms of PN during EV-based therapy.

3-2. Secondary Objectives

(1) To evaluate the relationship between patient characteristics/neurological function changes and patient-reported PN in order to identify high risk patients for developing PN during EV-based therapy.

(2) To investigate the correlation between neurological function changes and oncological outcomes of EV-based therapy, including objective response rate (ORR), progression-free survival (PFS), and overall survival (OS).

4. Study Design

4-1. Study Type: Observational

4-2. Study Design: Prospective cohort study

4-3. Study Center: Single-center (National Taiwan University Hospital, NTUH); may expand to multi-center in the future

4-4. Enrollment Method: Consecutive enrollment of eligible patients

4-5. Study Period: July, 2025 to December 31, 2031

4-6. **Estimated Sample Size:** 100 patients receiving EV-based therapy

5. Study Population

5-1. Inclusion Criteria

- (1) Age \geq 20 y/o
- (2) Histologically confirmed urothelial carcinoma
- (3) Radiologically documented locally advanced or metastatic disease
- (4) Prepare for receiving EV (as monotherapy or in combination with immune checkpoint inhibitors)
- (5) Complete and identifiable medical records

5-2. Exclusion Criteria

- (1) Do not agree to receive regular neurological examinations
- (2) Do not agree to provide complete medical records during treatment

5-3. Sampling Method

- (1) Consecutive enrollment of eligible patients meeting the inclusion criteria

6. Study Groups/Cohorts

6-1. Group 1: EV-based Therapy Cohort

- (1) Population: Patients with locally advanced or metastatic urothelial carcinoma receiving EV-based therapy
- (2) Diagnostic test: Neurological evaluations including neurological examination (NE), nerve conduction study (NCS), quantitative sensory testing (QST), autonomic function testing (AFT), and the Toronto Clinical Neuropathy Score (TCNS) questionnaire. Assessments will be conducted at baseline and every three months until six months after completion of EV treatment.

7. Endpoints / Outcome Measures

7-1. Primary Outcome Measure

(1) Correlation between neurological function and subjective PN symptoms:

Correlation between objective neurological assessments (including NE, QST, AFS, and TCNS) and patient-reported PN symptoms.

Time Frame: Baseline to 6 months post-treatment.

7-2. Secondary Outcome Measure

(1) Correlation between neurological function changes and oncological outcomes: To evaluate whether the degree or pattern of neurological function changes (e.g., worsening in NCS, QST) correlates with clinical efficacy measures such as ORR, PFS, and OS.

Time Frame: From date of EV initiation to the date of death from any cause, assessed up to 36 months

8. Methods / Assessments

8-1. Neurological assessment

(1) NE

(2) NCS

(3) QST

(4) AFT

(5) TCNS

All of these neurological function assessment will be evaluated as baseline , every three month during treatment, up to 6 months after completion of treatment.

8-2. Data Collection

Demographic, clinical, and treatment-related data will be recorded, including age, sex, comorbidities, ECOG performance status, prior treatments, EV regimen details, and cumulative dose. Patient-reported outcomes (PN symptoms) and oncological outcomes (ORR, PFS, OS) will also be collected.

8-3. Statistical Analysis

(1) Descriptive statistics will be used to summarize patient characteristics.

(2) Survival analysis:

- Kaplan–Meier method for estimating PFS and OS
- Log-rank test for between-group comparisons

(4) Multivariable analysis:

- Cox proportional hazards model to assess the independent association of neurological function factors with survival outcomes
- Logistic regression for associations with objective response

9. Ethics / Regulatory Compliance

9-1. The study protocol has been reviewed and approved by the Research Ethics Committee B of National Taiwan University Hospital.

IRB Approval Number:202502005RINB

Approval Date: 2025-03-13

9-2. This study will be conducted in accordance with the principles of the Declaration of Helsinki, ICH Good Clinical Practice (GCP) guidelines, and applicable local regulatory requirements.

9-3. Informed consent will be obtained from all participants before enrollment. The consent process will include information on study purpose, procedures, risks, benefits, data confidentiality, and the voluntary nature of participation.

9-4. Confidentiality and data protection:

- (1) All personal identifying information will be coded and stored securely in password-protected databases.
- (2) Only authorized study personnel will have access to identifiable data.
- (3) Data will be reported in aggregate to prevent the identification of individual participants.

10. Study Timeline

10-1. Planned Study Start Date: Jul, 2025

10-2. Planned Study End Date (Final Data Collection): December 31, 2031

10-3. Primary Completion Date: December 31, 2030

10-4. Study Completion Date: December 31, 2031

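### Neurological change seen only after baseline is to be related to PFS and OS timed from EV start, with no landmark or time-dependent covariate, leaving the analysis open to guarantee-time bias

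*Protocol*

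**What the plan says.** Secondary objective 3-2(2) is "To investigate the correlation between neurological function changes and oncological outcomes of EV-based therapy". The matching outcome in 7-2 is to evaluate "whether the degree or pattern of neurological function changes (e.g., worsening in NCS, QST) correlates with clinical efficacy measures", namely ORR, PFS and OS, with "Time Frame: From date of EV initiation to the date of death from any cause, assessed up to 36 months".

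Section 6-1(2) sets the test schedule: "Assessments will be conducted at baseline and every three months until six months after completion of EV treatment".

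For survival, section 8-3 names Kaplan-Meier estimation, "Log-rank test for between-group comparisons" and "Cox proportional hazards model to assess the independent association of neurological function factors with survival outcomes". For response it names "Logistic regression for associations with objective response". The groups for the log-rank test are not defined, and the study has a single cohort. The protocol mentions no landmark, no time-dependent covariate and no fixed time by which change is to be classified.

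**The concern.** The exposure is a change, so it does not exist at baseline. The first visit that can show it is at about month 3, and how long testing lasts depends on how long EV lasts. The survival clock starts earlier, at EV initiation.

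A patient classed as worsened must have stayed alive, and in most cases on treatment, long enough to worsen and be tested. Patients with early events fall into the unworsened group by default. Comparing the two groups from EV start therefore favours the worsened group even if neuropathy has no bearing on outcome.

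For response the mechanism is different and is not guarantee time. Responders stay on EV, and under testing, for longer, so they have more opportunity to worsen.

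Secondary objective (2) could then report that EV neuropathy predicts better PFS, OS or response when the association comes only from follow-up or treatment time. The protocol wants to weigh efficacy against tolerability, and such a result would mislead that judgement.

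**Working it through.** The protocol gives no effect size, alpha or event count for this outcome, so there is no figure to reproduce. The check asks what the listed methods return when worsening truly has no effect.

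**Inputs from the protocol.** 100 patients (4-6); tests every three months until six months after EV (6-1); 36-month cap (7-2); "PN occurs in 40–50% of patients" (section 2), used as a stand-in for the share with detected worsening.

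**Assumptions not in the protocol.** Exponential progression-or-death time with median 6, 9 or 12 months, paired with post-progression survival medians of 8, 12 or 15 months (OS median 15-29 months). 15% of PFS events are deaths. EV stops at progression. Tests are two-sided at 5%.

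**Method.** Illness-death simulation with 1500 replicates per cell. Onset is drawn independently of outcome and detected at the next 3-monthly visit, if that falls within six months of EV stop and before death or month 36. The onset rate is calibrated to 40% or 50% detected. Ranges are the minimum and maximum over six cells (3 median pairs × 2 shares) of the median HR, with the false-positive rate in brackets.

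**Fixed ever-worsened coding, time from EV start, no true effect:**

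| Onset pattern | PFS HR | OS HR |
|---|---|---|
| (a) any time on EV | 0.25-0.34 (100%) | 0.42-0.49 (85-93%) |
| (b) also in the 6 months after EV | 0.38-0.45 (95-100%) | 0.46-0.51 (77-94%) |
| (c) first 6 months, on EV only | 0.47-0.71 (33-95%) | 0.62-0.74 (18-63%) |
| (d) first 6 months, regardless of EV stop | 0.78-0.91 (7-23%) | 0.74-0.86 (9-30%) |

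Pattern (c) depends on the shape of onset. The figures shown fit onset spread evenly over the six months; with a constant onset hazard the PFS HR was milder, about 0.54-0.73.

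**Alternatives under the same four patterns:**
- PFS, time-dependent Cox: HR 0.97-1.01 (4-6%).
- PFS, 3-month landmark: 0.98-1.04 (4-7%).
- OS, 3-month landmark among patients alive: 0.93-1.04 (5-7%).
- OS, time-dependent Cox alone: still 0.72-0.77 (15-23%) under (a), because onset stops at progression. Stratifying by current progression status gives 0.98-1.01 (4-6%) in all four patterns.

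A simpler simulation with one event type and a constant worsening hazard (event medians 6-30 months, 2000 runs per scenario) gave HR 0.17-0.38 with 94-100% false positives for ever-worsened coding. Time-dependent Cox gave 0.99-1.01 (4.1-6.0%), and a 6-month landmark gave 0.98-1.02 (4.5-6.3%).

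**Response.** Let treatment time be exponential with rate a in responders and b in non-responders, with the same PN hazard h in both. The probability of PN before EV stops is h/(h+a) or h/(h+b), so the odds are h/a and h/b. The null OR is (h/a)/(h/b) = b/a, the ratio of mean treatment times. It is 1.0 at equal time, 1.5 at 1.5 times (14-17% false positives) and 3.0 at 3 times (70-76%), for an assumed ORR of 40-60%. Counting change only up to month 3 gives an OR of 1.06-1.07 (3-5%) and 1.20-1.32 (3-9%) at those two ratios.

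**The case against.** The strongest reply is that the biased analysis is not written down. Section 8-3 is a short method list, and coding rules are usual SAP content. Cox models admit time-dependent covariates, and the log-rank groups could be baseline groups such as monotherapy versus combination. Degree of change could also mean change at one fixed visit. When change at month 3 was entered as a fixed covariate in patients alive then, with time still counted from EV start, the null PFS HR was 0.83-1.05 (4-14%) and the OS HR 0.92-1.02 (3-8%), so bias was small or absent.

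This stands as far as it goes: the large figures belong to ever-worsened coding and should not be read as what the trial will produce. Some further limits also stand. The protocol's 40-50% is occurrence of PN, not of NCS or QST worsening. The simulation has no EV stop caused by neuropathy, although section 2 calls it dose-limiting. The origin for PFS and OS is read from the 7-2 time frame, since the protocol defines none separately.

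It does not remove the point. The protocol itself pairs a post-baseline exposure and a clock from EV start with a log-rank test between groups, in a cohort with no other groups defined. Grouping by observed change is the obvious reading, and a log-rank test from EV start on that grouping is not valid.

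**Conclusion.** The concern holds. As written, 7-2 and 8-3 leave secondary objective (2) open to a spurious protective association between neuropathy and PFS or OS, and to a related exposure-time artefact for response.

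If patients are coded by change seen at any time in follow-up, the false signal ranges from severe (onset throughout treatment) to modest (early onset with testing that continues after EV stops). It could vanish if nearly all onset is early and testing continues after progression. These sizes rest on the assumed medians, onset patterns and stopping of EV at progression; the bias favoured worsening in every pattern run with that coding.

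This should be fixed before analysis. Analyses by baseline neurological function or other baseline groupings, and the primary outcome, are not affected.

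**What to change.** State in section 8-3:

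1. In the Cox models for PFS and OS, post-baseline neurological change enters as a time-dependent covariate updated at each 3-monthly visit, with a rule for its value once testing has ended. For OS, also report the model with progression status as a time-dependent covariate or stratum.
2. Kaplan-Meier curves and log-rank tests by neurological change use only a landmark at the 3-month visit. They include patients alive and progression-free for PFS, or alive for OS, grouped by change up to that visit and timed from it.
3. For response, use baseline neurological values or change within a fixed window, for example up to the 3-month visit, and not ever-worsened or worst change.

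This is a change of wording that uses visits already scheduled. The landmark ignores later change and drops patients with earlier events. For PFS that share is 1 − 2^(−3/median), which is 29%, 21% and 16% at assumed medians of 6, 9 and 12 months; for OS it is 3-8% under the assumptions above. Adjusting OS for progression removes any effect that acts through progression, so both OS models should be shown.
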